	 Atypical or secondary Parkinsonism without dopa-sensitivity (e.g., vascular parkinsonism, supranuclear palsy, multisystem atrophy) 		
	 Progressing Axis I psychiatric disorders (psychosis, hallucinations, compulsive disorders, substance addiction, bipolar disorder, severe depression, anxiety) as assessed in a semi-structured interview in accordance with the Diagnostic and Statistical Manual of Mental Disorders 		
	Not stabilized in terms of the current antiparkinsonian therapeutic regimen: already requires dose adaptation and/or is likely to require any change in dopamine therapy over the duration of the trial		
	Current treatment with bromocriptine		
	Current treatment with any antiparkinsonian drug other than those listed in the inclusion criteria		
	• Current treatment with coenzyme Q10 or idebenone. (Patients who are on these medications but stop taking them at least 2 weeks prior to baseline may be enrolled.)		
	Current use of a Deep Brain Stimulation (DBS) system. (Patients who previously had a DBS system but have had it removed may be enrolled.)		
Investigational	Product: Deferiprone delayed release 600 mg bisectable tablets		
product:	Dose: 300 mg, 600 mg, 900 mg, or 1200 mg b.i.d., for a total daily dosage of 600 mg, 1200 mg, 1800 mg, or 2400 mg		
	Mode of administration: Oral		
Reference product:	Product: Placebo		
	Dose: Number of tablets matching that required for a 300, 600, 900, or 1200 mg dose of active product		
	Mode of administration: Oral		

Schedule of treatment and assessments:

Treatment

All patients will take the assigned study medication at specified times twice daily, at least 8 hours apart, for 9 months.

Efficacy assessments

- The MDS-UPDRS and MoCA will be completed at baseline and Months 3, 6, and 9
- Blood samples for the assessment of pharmacodynamics biomarkers and of the MOA biomarkers of total antioxidant status protein carbonyls, glutathione, and super-oxide dismutase will be collected at baseline and Months 3, 6, and 9
- Urine samples for the assessment of the oxidative stress biomarkers 8-OHdG and lipid peroxidation (malondialdehyde) will be collected at baseline and Months 3, 6, and 9

Note: The MDS-UPDRS and MoCA are to be administered early in the morning, at approximately the same time (\pm 1 hour) at each visit, and by the same qualified investigator.

Safety assessments

- Hematology: Screening and weekly after the start of dosing up to Month 9
- Blood chemistry: Screening and Months 1, 2, 3, 4, 5, 6, and 9

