1.4 Potential Risks and Benefits

Risks: The safety profile of deferiprone has been extensively characterized in patients with systemic iron overload. The most serious adverse event associated with its use in that population is severe neutropenia or agranulocytosis, defined as a confirmed absolute neutrophil count (ANC) less than 0.5×10^9 /L. In pooled clinical trials, agranulocytosis has been seen in about 2% of patients. The mechanism of deferiprone-associated agranulocytosis is unknown. Agranulocytosis usually resolves upon discontinuation of deferiprone, but there have been post-marketing reports of it leading to death. Accordingly, deferiprone recipients are required to undergo weekly hematology testing to ensure early detection of a drop in ANC. The most common non-serious adverse reactions reported during clinical trials have been chromaturia (due to iron excretion), nausea, vomiting, abdominal pain, increased alanine aminotransferase, arthralgia, and mild or moderate neutropenia (ANC less than 1.5×10^9 /L). The safety profile observed so far in patients with local iron overload has been found to be similar to that seen in the population with systemic iron overload, with respect to major risks. For detailed information on adverse events associated with deferiprone, see the Investigator's Brochure.

Benefits: The findings of preclinical and clinical research suggest that deferiprone has the potential to access pathologically relevant brain iron and to produce clinical benefit in patients with Parkinson's disease. The currently available medications for PD act only on symptoms, not on the underlying cause of the disorder. This treatment may possibly act to prevent the cell death that gives rise to those symptoms.

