4.3 Exclusion Criteria

Individuals will be excluded from enrollment if they meet any of the following criteria:

- 1. Diagnosis of Parkinson's disease more than 3 years prior to screening visit
- 2. Hoehn and Yahr stage ≥ 3
- 3. Atypical or secondary Parkinsonism without dopa-sensitivity (e.g., vascular parkinsonism, supranuclear palsy, multisystem atrophy)
- 4. Progressing Axis I psychiatric disorders (psychosis, hallucinations, compulsive disorders, substance addiction, bipolar disorder, severe depression, anxiety) as assessed in a semi-structured interview in accordance with the Diagnostic and Statistical Manual of Mental Disorders
- 5. Not stabilized in terms of the current antiparkinsonian therapeutic regimen: already requires dose adaptation and/or is likely to require any change in dopamine therapy over the duration of the trial
- 6. Current treatment with bromocriptine
- 7. Current treatment with any antiparkinsonian drug other than those listed in inclusion criterion #5
- 8. Current treatment with coenzyme Q10 or idebenone. (Patients who are on these medications but stop taking them at least 2 weeks prior to baseline may be enrolled.)
- 9. Current use of a Deep Brain Stimulation (DBS) system. (Patients who previously had a DBS system but have had it removed may be enrolled.)
- 10. History of malignancy, with the exception of cancers that have been in remission for ≥5 years at the time of screening
- 11. Evidence of abnormal liver or kidney function at screening (serum ALT level > 5 times upper limit of normal or creatinine levels >2 times upper limit of normal)
- 12. A serious, unstable illness, as judged by the investigator, during the past 3 months before screening visit, including but not limited to hepatic, renal, gastro-enterologic, respiratory, cardiovascular, endocrinologic, or immunologic disease

- 13. Disorders associated with neutropenia (ANC < 1.5×10^9 /L; < 1.0×10^9 /L in Black population) or thrombocytopenia (platelet count < 50×10^9 /L) in the 12 months preceding the initiation of the study medication. Exception: For patients whose neutropenia is attributed by the treating physician to episodes of infection or to drugs associated with a decline in the neutrophil count and in whom the ANC is back to a normal level at the screening visit.
- 14. Clinically significant abnormalities on 12-lead ECG, as judged by the investigator
- 15. Myocardial infarction, cardiac arrest, or cardiac failure within 1 year before screening visit

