7.2.1.8 Adverse Events of Special Interest

7.2.1.8.1 Neutropenia

Individuals taking deferiprone must be monitored for neutropenia, defined as a confirmed absolute neutrophil count (ANC) less than 1.5×10^9 /L. Categories of neutropenia are as follows:

Category	Black Population	All Other Races
Mild	A confirmed ANC $< 1.0 \times 10^9/L$ but $\ge 0.65 \times 10^9/L$	A confirmed ANC $< 1.5 \times 10^9$ /L but $\ge 1.0 \times 10^9$ /L
Moderate	A confirmed ANC $< 0.65 \times 10^9/L$ but $\ge 0.5 \times 10^9/L$	A confirmed ANC $< 1.0 \times 10^9$ /L but $\ge 0.5 \times 10^9$ /L
Severe/agranulocytosis	A confirmed ANC $< 0.5 \times 10^9 / L$	

For a case of neutropenia to be confirmed, there must be 2 consecutive counts, a maximum of 3 days apart, that are both less than the specified value. If the 2 counts are not in the same severity category, a third count will be required to determine the severity. If a patient has just a single ANC value less than $1.5 \times 10^9/L$ ($< 1.0 \times 10^9/L$ for a black patient), this is to be documented in the CRF as an AE of "decreased ANC", but is not to be defined as neutropenia. The investigator is to use judgment as to whether the decrease is clinically significant.

In addition to having ANC monitored, patients will be advised to immediately report any symptoms indicative of infection such as fever (≥ 38.5 °C), sore throat, and flu-like symptoms at any time during treatment or during the first week following treatment. They will be

provided with an emergency services card with contact information, and advised to carry it with them at all times.

Depending of the severity of neutropenia, patients will either remain in or be withdrawn from the study. The management of different severities of neutropenia is described below.

Mild and moderate neutropenia:

A patient who develops either mild or moderate neutropenia is to interrupt treatment as soon as the neutropenia is confirmed, and ANC is to be monitored every 2 days until resolution.

The patient should re-initiate treatment once the event is resolved, defined as 2 consecutive ANC $\geq 1.5 \times 10^9$ /L (ANC $\geq 1.0 \times 10^9$ /L for a black patient). If ANC is still $< 1.5 \times 10^9$ /L after 14 days, the investigator is to do the following:

- Withdraw patient from the study and monitor him/her until resolution of the event
- Advise patient regarding protective isolation

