7.2.1.8.2 Infections

If a patient develops fever (\geq 38.5°C) or any sign of infection during the study, deferiprone must be interrupted immediately, and neutrophil count should be obtained and monitored more frequently; every 2 days if ANC <1.5 x 10^9 /L (ANC < 1.0 x 10^9 /L for a black patient). Therapy with deferiprone can be re-initiated once all symptoms have been resolved and it is deemed safe by the investigator.

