and within each SOC, the preferred term will be presented in decreasing order of the total number of patients who experienced each AE. In summaries presenting the incidence of AEs by severity, seriousness, and relation to study medication, a patient with multiple events coded to a given PT or SOC will be counted only once for that PT or SOC according to the most severe event, the most serious event, or the event with the closest relationship to study medication.

Listing of SAEs and listing of withdrawals due to AEs will be presented. Patient deaths will be listed separately, and will be described in narratives.

Vital Signs and Weight

Descriptive statistics (mean, median, standard deviation, minimum and maximum) will be presented at each visit for supine and standing heart rate, supine and standing blood pressure, body temperature, and weight. Data will also be presented graphically for examination of possible trends. Change from baseline in vital signs (at baseline, the values for orthostatic vital signs will be the average of the three sets collected) and weight will be assessed.

Electrocardiogram

The number and percentage of patients with normal and abnormal ECG results will be provided. Descriptive statistics will be presented for HR, PR, QRS, QT, QTcF, and QTcB.

Biochemistry, Hematology and Urinalysis

Descriptive statistics for each clinical laboratory test will be presented for each scheduled visit. According to the laboratory normal ranges, laboratory test results will be categorized as low (< lower normal limit), normal (within normal range), and high (> upper normal limit). Shift tables comparing the distributions of these three categories at baseline versus end of treatment will be presented. Continuous data will also be presented graphically for examination of possible trends.

Clinically significant laboratory values will be reported in the adverse event analysis.

Concomitant Medications

Medications will be coded using the WHO Drug Dictionary. Medications taken during the course of the trial (on or after the first study drug dose and before or on the study termination date) will be considered as concomitant medications. Medications started after the study termination date will not be reported in tables, but will be presented in listings. Concomitant medications that were used to treat adverse events will be differentiated from others.

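### Laboratory shift tables set baseline only against end of treatment, so abnormalities that resolve during treatment do not appear in them

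*Protocol*

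**What the plan says.** Section 9.4.1.4 (Biochemistry, Hematology and Urinalysis) sets the categories, "According to the laboratory normal ranges, laboratory test results will be categorized as low (< lower normal limit), normal" or high, and then the comparison: "Shift tables comparing the distributions of these three categories at baseline versus end of treatment will be presented". No table of the worst value on treatment is specified. The same section also plans descriptive statistics at each scheduled visit and graphs of continuous data, and it carries clinically significant values into the adverse event analysis. All safety data are to be listed.

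Sampling is much denser than the shift table uses. The Synopsis has "Hematology: Screening and weekly after the start of dosing up to Month 9", and chemistry at screening and Months 1 to 6 and 9.

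Section 7.2.1.8.1 says what happens when the ANC falls: "A patient who develops either mild or moderate neutropenia is to interrupt treatment as soon as the neutropenia is confirmed". After ANC checks every 2 days, "The patient should re-initiate treatment once the event is resolved". Resolution means two consecutive counts at or above the threshold. A patient not resolved after 14 days, or with a confirmed ANC below 0.5 x 10^9/L, is withdrawn. The section grades neutropenia as mild, moderate or severe, with separate mild and moderate limits for Black patients. It also requires a single count below the threshold to be recorded as an adverse event.

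**The concern.** A shift table is read as a summary of how many patients moved out of range, by treatment group. With end of treatment as the only comparison point, it reports how many were out of range on one occasion. A patient whose neutropenia was handled as the protocol directs will normally have recovered by then.

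This is also the only categorical laboratory summary in the protocol that does not depend on the investigator's judgement of clinical significance. Section 3.3 makes the balance of benefit and toxicity across four doses the purpose of the study, with 28 patients per dose. Section 1.4 lists among the common reactions "nausea, vomiting, abdominal pain, increased alanine aminotransferase, arthralgia, and mild or moderate neutropenia". A table that is blind to resolved changes is a weak tool for comparing doses on laboratory effects of that kind.

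**Working it through.** The protocol gives no figure to reproduce here. The check compares the sections and adds an illustration.

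**What the table uses.** Nine months is about 9 x 30.4 = 274 days, or 274/7 = about 39 weekly hematology draws. The shift table uses one of them. For chemistry it uses one of seven post-baseline visits.

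**What else would show the change.**

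| Change | Shift table | Adverse event tables | Other outputs |
|---|---|---|---|
| Mild or moderate neutropenia, resolved | not shown | yes, recording is mandatory (7.2.1.8.1) | listings; by-visit statistics if the draw counts as a scheduled visit |
| ALT, creatinine or platelet shift, resolved, marked clinically significant | not shown | yes, unless part of a condition already recorded (7.2.1.1, 7.2.2) | by-visit statistics, graphs, listings |
| The same, marked not clinically significant | not shown | no | by-visit statistics, graphs, listings |

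The third row is the real gap. By-visit means and medians do not show how many individual patients crossed a limit. For ANC and platelets, most weekly draws fall between the site visits (Months 1 to 6 and 9), so the scheduled-visit statistics may not include them.

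**How often a resolved episode shows at the end.** Assume one episode of length L days, onset uniform over 274 days, in a patient who stays on treatment to Month 9. The share still present at the end is L/274.

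- L = 7: 7/274 = 2.6%
- L = 14: 14/274 = 5.1%

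The protocol gives no episode lengths, so these are assumptions. For neutropenia, 14 days is a natural upper value because patients not resolved after 14 days leave the study.

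**What a worst-value table would add for chemistry.** Place the visits at days 30, 61, 91, 122, 152, 183 and 274. An episode is seen at a visit if it starts within the L days before that visit.

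| Assumed length | Present at some visit | Present at the end |
|---|---|---|
| 14 days | 7 x 14 / 274 = 36% | 14/274 = 5% |
| 28 days | 7 x 28 / 274 = 72% | 28/274 = 10% |
| 60 days | (183 + 60) / 274 = 89% | 60/274 = 22% |

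In the last row the windows before the first six visits merge to cover days 0 to 183, and the Month 9 window adds 60 days.

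**Categories.** The table uses laboratory normal ranges, while Section 7.2.1.8.1 uses fixed ANC limits. The protocol does not give the laboratory limits, and weekly counts may come from local laboratories (7.2.2). A low ANC in the table therefore need not match any protocol grade of neutropenia.

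**The case against.** The case on the other side is that this is one descriptive table among several outputs. That is largely right for neutropenia. A reader might infer that neutropenia is lost from the safety analysis, or is reported only at the investigator's discretion. The protocol does not support this: even one low count must be recorded as an adverse event, and judgement concerns only its clinical significance. Neutropenia is also an event of special interest, and adverse events are counted by treatment group and by intensity. Episodes stay countable by dose.

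A reader might also infer that liver-enzyme rises resolve because treatment is interrupted for them. No such rule exists. Interruption is required for neutropenia and for fever or infection (Section 7.2.1.8.2: "deferiprone must be interrupted immediately, and neutrophil count should be obtained and monitored more frequently"). The only ALT limit is a screening exclusion, "serum ALT level > 5 times upper limit of normal". A passing ALT rise is missing from the table simply because it has resolved.

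Finally, a reader might conclude that nearly all neutropenia of any severity is hidden. The random-onset calculation does not reach severe or prolonged cases. There the episode itself ends treatment, so its timing relative to the end is not random. Whether such a case shows depends on which value counts as end of treatment, which Section 9.4.1.4 leaves open; the early termination visit may come up to a month after withdrawal.

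It can also be said that the unseen SAP may add a worst-value table. It may. But Section 9.4 says the SAP will detail the specifications given in the protocol, and the one given is baseline against end of treatment.

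**Conclusion.** The point holds for the laboratory shift table and no further. As specified, the table cannot show mild or moderate neutropenia that resolved under the protocol's interruption and restart rule, or any ALT, creatinine or platelet shift that passed before the last sample. The practical loss is moderate to small. It lies mainly in shifts marked not clinically significant and in weekly values outside the scheduled-visit summaries.

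The 3% to 5% visibility figure rests on assumed lengths of 7 to 14 days, random onset, about 274 days of treatment, and a patient who completes it. The chemistry percentages rest on nominal visit days and assumed durations. Neither is an estimate of how many events will occur.

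**What to change.** Add a shift table of baseline against the worst post-baseline value, by treatment group: lowest ANC and platelets, highest ALT and creatinine. Take the worst value over all scheduled, weekly and unscheduled samples. Categorise ANC by the Section 7.2.1.8.1 limits, including those for Black patients, and show single unconfirmed low values separately from confirmed neutropenia. Keep the end-of-treatment table as the second table, and state which value counts as end of treatment for patients who withdraw.

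The cost is one more table specification, plus a rule for handling local-laboratory ranges. No new samples are needed and no clinical procedure changes.

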9.4.1.5 Pharmacokinetics Analyses

The pharmacokinetics parameters will be summarized using descriptive statistics (arithmetic mean, SD, CV, median, minimum and maximum values). The power model will be used for assessing dose proportionality of AUC. Actual sampling times will be used for pharmacokinetic evaluations. Relationships will be assessed between the appropriate PK parameters and pharmacodynamics biomarkers through correlation analysis.

Additional pharmacokinetics analyses may be performed if deemed appropriate.

Detailed analyses on PK assessments and pharmacokinetics/pharmacodynamics assessments will be included in separate statistical analysis plans.

9.4.2 Interim Analyses

No interim analysis is planned.

9.5 Criteria for Evaluability of Patient Data

Statistical analysis will be based on the study populations defined in Section 9.3.

10 DATA MANAGEMENT CONSIDERATIONS

10.1 Data Management

The sponsor's Clinical Data Management group will be responsible for the processing, coding, and validating/cleaning of clinical study data. Patient data will be entered by the investigator or designee using the electronic Case Report Forms (eCRFs) provided by the sponsor. Clinical data will be entered and stored into a validated database. The eCRFs will be provided in the Electronic Data Capture (EDC) system hosted by the sponsor. Trained users will access the system via a secured gateway. Users will be only authorized to access data for their study site. Data will be entered directly into the system from the source documents in lieu of the paper CRFs. On-line and off-line edit checks will be used to prompt the user to provide clean and accurate data. Clinical Data Management will code and monitor the data

for accuracy. The data will be coded using the current versions of the MedDRA (Medical Dictionary for Regulatory Activities) and WHODD (World Health Organization Drug Dictionary) dictionaries. An electronic signature will be required of the investigator on the eCRFs, and the study monitor will verify the eCRFs on-line.

Clinical data management activities will be performed by the sponsor in accordance with applicable standards and data cleaning procedures of the sponsor. An audit trail of all data processing will be stored in the database. The study biostatistician will be notified when all patient data are ready for analysis.

Integrity of the database will be assured by limiting access through username/password combination and account control. Authorized access to the database will be provided to those individuals with an inspection/auditing function (Regulatory Authorities/Quality Assurance); "read only" access will be provided to avoid unintentional corruption of the database.

The database will be backed up daily.

10.2 Case Report Forms

Electronic CRFs may be generated and/or printed at any time using the sponsor's EDC system. These eCRFs may be used for electronic submission data archiving or data review. A copy of the final patient-specific eCRFs will be sent to the clinical study sites after database freeze.

11 MONITORING, AUDITS, AND INSPECTIONS

11.1 Source Documents

The investigator or delegate will maintain adequately detailed source documents supporting significant source data for each patient. Source data are defined as all information in original records and/or certified copies of original records of clinical findings, observations, or other activities in a clinical study that are necessary for the reconstruction and evaluation of the study: e.g., medical history, physical examination, laboratory results, and x-ray or ultrasound results. The investigator will also retain all printouts/reports of tests or procedures performed as a requirement of the study. All source data that is printed on thermal paper, including laboratory printouts and ECGs scans, must be photocopied, initialed, and dated as authentic equivalents to the thermal paper documents to enable extended retention time.

The source documents must be available at the time of an audit; a site visit from the sponsor, sponsor representatives, or IRB/IEC; and a regulatory authority inspection.

